[Part 7 of 7 of the document. The other parts are not shown.]

Subjects with mild AD recruited in Stage B will be assessed as a “nested” population that does not follow the Bayesian adaptive design. It was not considered appropriate to have a Bayesian design for both cohorts as this would have substantially increased the overall study sample size, delayed analyses of dose response, and would have added background “noise” for the comparison of subjects with MCI/Prodromal AD compared with those with mild AD. Data from each cohort will be analyzed independently for the purposes of decision making. A separate analysis of the 2 cohorts avoids the risk of data from subjects with mild AD confounding the results for the primary population (MCI/prodromal).

9.2.4 Rationale for Clinical Endpoints

The ADCOMS (Hendrix, et al., 2012) was developed utilizing data from multiple studies to investigate responsiveness to progression and treatment effects rather than sensitivity to baseline deficits. The score was built empirically with no a priori assumptions, using a partial least squares regression model for placebo data from 4 MCI studies with a duration ≥ 12 months. A combination of cognitive and functional items was selected from a variety of well-established and validated scales that is most sensitive to change over time. The partial least squares regression coefficients from the model were used to form a weighted composite

score comprising a total of 12 individual items taken from the ADAS-cog (4 items), the MMSE (2 items), and CDR (6 items), that assess both cognition and global function. Performance of the ADCOMS has been assessed against the original scales in several studies. The use of the ADCOMS allows for substantial sample size reductions in non-enriched and enriched MCI populations even over a 12-month period by increasing sensitivity. This derived score has shown adequate sensitivity in the MCI due to AD amyloid confirmed (CSF A β -positive) subgroup.

The ADAS-Cog is the most widely used cognitive scale in AD clinical studies (Rosen, et al., 1984). The 14-item version will be used in the present study since it is considered more sensitive for less impaired populations such as MCI/Prodromal and mild AD subjects (Fleisher, et al., 2007).

The MMSE is a cognitive instrument commonly used for screening purposes, for staging of disease severity and is often measured longitudinally in AD clinical studies to follow disease progression and treatment effects (Folstein, et al., 1975).

The CDR is a clinical global rating scale requiring the interviewing of both the subject and an informant who knows and has contact with the subject. The CDR is a clinician-directed assessment of both cognition and function, and is intended to capture the state and therefore the disease stage of the individual. The CDR has been proposed as an acceptable approach for following disease progression and confirming treatment in AD.

The FAQ collects information on 10 items concerned with performing daily tasks necessary for independent living. The FAQ is considered as a better indicator of clinical meaningfulness than cognitive change as it reflects the subject's functional state and should correlate well with AD progression.

The CBB is a brief, computer-administered cognitive test battery that requires approximately 10 minutes for administration (Darby, et al., 2012; Fredrickson, et al., 2008; Maruff, et al., 2009). The CBB has been used to detect cognitive impairment in several neurodegenerative conditions including the measurement of cognitive function in healthy older adults and in adults with clinically diagnosed AD and prodromal AD (Darby, et al., 2009; Hammers, et al., 2012; Lim, et al., 2012a; Lim, et al., 2012b). The administration, scoring, and reporting of the CBB is automated and highly standardized, resulting in cognitive paradigms that have been well-validated in neuropsychological and cognitive studies (Fredrickson, et al., 2008; Maruff, et al., 2009). See Section 9.5.1.3.1 for further details.

The ISLT is sensitive to memory impairment that characterizes both AD and MCI (Lim, et al., 2012a). In MCI subjects, the magnitude of the impairment observed on the total recall and delayed recall trials on the ISLT was consistent with the magnitude of impairment expected to occur. It is sensitive to the episodic memory impairment that characterizes MCI with high amyloid (unpublished data from the Australian Imaging, Biomarker and Lifestyle Flagship Study of Ageing study). Data are robust across different groups of healthy older individuals, and accordingly criteria used for defining abnormal performance are reliable (Thompson et al., 2011, Lim, et al., 2012a, Lim, et al., 2012b). Data computations indicate

that the ISLT will be sensitive to the expected changes in amyloid-related memory dysfunction with E2609 treatment.

Volumetric magnetic resonance imaging is discussed in [Section 9.2.5.4](#).

9.2.5 Rationale for Biomarkers

9.2.5.1 Overall Rationale

The biomarker strategy for this study includes the following aims:

- To establish an amyloid load in the brain at study entry (via the PET eligibility inclusion criterion)
- To evaluate safety (principally by magnetic resonance imaging [MRI])
- To confirm a PD effect in terms of both A β in CSF and brain amyloid assessed by PET and to establish that this PD effect is maintained long-term
- To evaluate disease modification through longitudinal assessments of vMRI, amyloid PET, and CSF biomarkers of neurodegeneration (tau and p-tau)

These aims are discussed below in the context of the individual biomarker assessments to be used in this study.

9.2.5.2 Soluble Biomarkers in CSF

A β (1-x) captures the effect on the total A β component; therefore, the measurement of this A β isoform most appropriately represents the total pharmacologic effect of E2609 on A β (1-40) + A β (1-42) and other C-terminally truncated A β peptides such as A β (1-38) through inhibition of BACE enzyme cleavage.

A β (1-42) measurements in CSF have shown high correlation with results using [¹¹C]PiB, suggesting that CSF A β (1-42) reflects fibrillar A β content ([Grimmer, et al., 2009](#)). The aggregation of A β peptides into plaques, and subsequent retention of peptides in the brain parenchyma, accounts for reduced availability of A β to diffuse into the CSF. The decreases in CSF A β concentrations that are seen in AD are believed to be related to this decrease in brain A β availability.

Both total tau (t-tau) and p-tau are sensitive markers of axonal and neuronal degeneration (t-tau) and neurofibrillary tangles (p-tau), and have been demonstrated to increase in parallel with disease progression ([Chintamaneni and Bhaskar, 2012](#)). CSF tau measurements have been correlated with cerebral atrophy, while their ratios with A β 42 have provided useful predictors of cognitive decline and progression to dementia due to AD. Rebalancing dysregulated amyloid production early in the process may positively affect the neurodegenerative process and thus affect these markers and benefit the disease trajectory. Therefore, monitoring these markers in conjunction with amyloid imaging may provide further supportive evidence of efficacy.

Baseline levels of A β (1-42), tau, and p-tau will also help elucidate the extent of AD pathology at entry to the study and can be combined with baseline levels of *ApoE4* genotyping in addition to the baseline imaging variables to help explain differences in treatment response.

The study will be stratified at randomization for *ApoE4* gene status in order to account for any *ApoE* status by treatment interaction or *ApoE* status by amyloid-related imaging abnormalities risk interaction.

9.2.5.3 Amyloid PET

Amyloid PET imaging will be performed in this study for 2 primary reasons: 1) to confirm the presence of AD pathology in the brain of subjects with MCI/Prodromal AD or mild AD at entry to the study; and 2) to evaluate the effects of E2609 on amyloid levels in the brain, both by whole brain analysis (the average of 5 to 6 cortical regions) and brain region analysis.

Longitudinal amyloid PET imaging will be conducted after 18 months of treatment (or at ED, providing the subject has received at least 39 weeks of study drug) as an exploratory measure of the potential disease-modifying effects of E2609. Longitudinal amyloid PET imaging will only be conducted until 18-month PET scans of acceptable quality have been obtained for at least 25 subjects per treatment arm for each amyloid PET ligand used.

9.2.5.4 vMRI

Volumetric imaging will be used to evaluate the effects of E2609 on rates of atrophy across the different dose groups and to provide support that effective treatment is associated with modification of disease course (secondary endpoint for the MCI/Prodromal population and exploratory endpoint for the Mild AD population). A large body of data has shown that structural MRI reliably tracks disease progression in AD. Atrophy tends to occur preferentially in the lateral temporal and posterior parietal regions during the early stages of disease and progresses towards the anterior regions of the brain (frontal cortex) in its later stages. Clinically efficacious doses are predicted to be associated with a slowing in the rate of hippocampal atrophy compared with rates observed in the placebo and non-efficacious dose groups. Treatment effects on left and right hippocampal, whole brain, and total ventricular volumes are exploratory endpoints.

Annualized rates of change of 2% to 3% have been reported for the AD brain compared with 1% in MCI and <1% in age-matched controls (Hua, et al., 2010, Leung, et al., 2010). However, subjects with MCI due to AD-dementia (CSF A β <192 pg/ml or positive amyloid imaging) show rates of atrophy comparable to those observed in subjects with AD-dementia (Hua, et al., 2009; Hua, et al., 2010; Leung, et al., 2010; Morra, et al., 2009), supporting the notion that such subjects are on similar trajectories as mild AD-dementia. Lower levels of CSF A β 42, amyloid positivity on PET imaging, and higher levels of CSF tau in addition to the presence of the *ApoE4* allele have all been associated with greater rates of brain atrophy (Fjell, et al., 2010a; Fjell, et al., 2010b) and will be entered as covariates in various analyses. Hippocampal atrophy has also been shown to predict clinical progression independently of

amyloid levels in the brain (Jack, et al., 2010), and this measure will be entered as a covariate in the analysis of the clinical endpoints along with the aforementioned variables.

Brain volume (total ventricular volume, whole brain, temporal lobe) generally shows a modest correlation with performance on a number of cognitive scales (Hua, et al., 2009; Hua, et al., 2010; Freeborough, et al., 1997; Leung, et al., 2010). Using volumetric analysis performed at 6-month intervals, these relationships and the effects of E2609 treatment will be explored further. Recent advances in analysis software have made structural imaging more sensitive to detect small changes and able to reliably measure rates of atrophy at these intervals, particularly in the posterior parietal and the lateral temporal regions during the early stages of disease (Hua, et al., 2009; Hua, et al., 2010). Given these observations, a demonstration of significant slowing or stabilization in the rate of atrophy in response to treatment, compared with placebo, will offer further support for disease modification.

9.2.6 Clinical Risks and Mitigation Strategy

A number of safety aspects have been built into the design of this study in light of the preclinical and clinical safety data with E2609, and to mitigate clinical risk in the progression from 14 days of dosing in the MAD study to 18 months of treatment in this Phase 2 study. These safety aspects include the following:

- Two-stage study design: there will be a pause in recruitment after 60 MCI/Prodromal subjects have been randomized to study drug (Stage A). Only after the safety of E2609 in these first 60 subjects (consisting of up to 12 weeks data for the later subjects and longer dosing periods for the earlier subjects) has been reviewed by the DSMB and considered acceptable, will randomization of further subjects into the study commence (Stage B).
- Immunology-related and infection-related exclusion criteria
- Review of unblinded safety data by an independent DSMB at regular intervals
- Safety criteria for discontinuation of study drug based on CD4 (T helper cells), CD8 (cytotoxic T cells), CD19 (B cell) and other lymphocytes (absolute counts and percentage change from baseline), skin rash, reoccurrence of herpes virus infections including any oral herpes, genital herpes or shingles, other infections, MRI changes, ECGs, and pregnancy.

In addition to the features above, other safety aspects of this study designed to mitigate clinical risk include the following:

- Blinded safety data will be monitored by Eisai at regular intervals during the course of the study
- Routine safety assessments will include the monitoring and recording of all AEs and SAEs, monitoring of hematology, blood chemistry, and urinalysis, measurement of vital signs, regular ECGs, physical and neurological examinations, and centralized dermatological assessments (via photography) at regular intervals. AEs that might indicate signals of possible drug abuse potential will require a detailed follow-up. Subjects reporting AEs relating to abnormal dreams, nightmares, or sleep terror will

be questioned on the frequency and impact of these events. To assess potential immunomodulatory effects, peripheral blood mononuclear cells (PBMCs) will be collected at baseline, during treatment, and posttreatment.

As per the communication from the Food and Drug Administration (FDA) in Aug 2013, there are concerns that hypopigmentation of the skin and mucous membranes may occur with BACE1 inhibitory drugs. Although no such effects have been seen with E2609 to date, assessments by a reviewing dermatologist will be performed at regular intervals during the study. These assessments will be made centrally, using standardized photography and will specifically include evaluation of any areas of depigmentation or any rash. Dermatological assessments will be supplemented with a specific question to subjects regarding skin changes at each visit. Any such changes could be referred to the central reviewing dermatologist, and to a local dermatologist if needed, for further evaluation. See [Section 9.5.1.5.8](#) for further details.

- Baseline and on-study blood, DNA, and CSF samples will be taken and stored for all subjects. These samples may be tested in the event that a subject develops AEs that warrant further investigation (eg, if a subject develops a treatment-emergent infection) (see [Section 9.5.1.2.2](#)).
- Central reading of safety brain MRI assessments (including any MRI evidence of demyelination) will be performed at Screening, at approximately 6-month intervals during the Treatment Phase of the study, and at the final Follow-Up Visit.
- Full neurological examinations will be performed at Baseline and at regular intervals during the study by either a neurologist or a physician with comparable training and experience in undertaking neurological examinations. Details of the neurological examination are given in [Section 9.5.1.5.9](#).
- Cognitive decline will be assessed as a safety assessment (ADAS-cog₁₄, MMSE, and CBB). Of particular importance will be the assessment of reaction time testing using the detection and identification tasks on the CBB.
- An assessment of suicidality using the C-SSRS will be performed at Screening, Baseline, and at regular intervals during the Treatment Phase and Follow-Up periods of the study (see [Section 9.5.1.5.11](#)).
- All subjects, regardless of whether they complete all 18 months of treatment or discontinue study drug prematurely, will have at least 2 off-treatment Follow-Up visits (4 and 12 weeks after the last dose of study drug). More frequent safety assessments can be made as unscheduled assessments/visits during the off-treatment Follow-Up period, if clinically indicated.
- An ophthalmic examination will be conducted at Baseline and if the subject experiences visual disturbances during the course of the study (see [Section 9.5.1.2.1](#)).

9.3 Selection of Study Population

Stage A will randomize 60 eligible MCI/Prodromal subjects at 25 centers in the United States. Stage B will randomize up to an additional 440 eligible MCI/Prodromal subjects at approximately 125 centers globally; the final total number will depend upon whether the

prespecified criteria for either early success or futility are met. In addition, a separate cohort of approximately 200 mild AD subjects will be randomized and dosed during Stage B.

Subjects who do not meet all of the inclusion criteria or who meet any of the exclusion criteria will not be eligible to receive study drug.

9.3.1 Inclusion Criteria

Subjects must meet all of the following criteria to be included in this study:

1. Meets the core clinical research criteria of the NIA-AA for MCI due to AD ([Albert, et al., 2011](#)) or AD dementia ([McKhann, et al., 2011](#)) and is "staged" or classified as either MCI (Stage A and Stage B) or mild dementia (Stage B only) and also complies with the following:

Required at both Screening and Baseline:

- a. Subjective Memory Complaint with evidence of concern about a decline in cognition from the subject, informant, or clinician's observation
 - b. Cognitive impairment of at least 1 SD from age adjusted norms in delayed recall on the ISLT
 - c. FAQ ≤ 20
 - d. MMSE ≥ 20
2. Amyloid positive PET image based on centralized PET scan reading
 3. Male or female, age 50 to 85 years, inclusive at time of consent
 4. Must have an identified caregiver or informant who is willing and able to provide follow-up information on the subject throughout the course of the study. This person must, in the opinion of the investigator, spend sufficient time with the subject on a regular basis such that the caregiver or informant can reliably fulfill the study requirements and must provide separate written consent. The caregiver or informant need not be living in the same residence as the subject. If the caregiver or informant is not residing with the subject, the investigator has to be satisfied that the subject can contact the caregiver or informant readily during the times when the caregiver or informant is not with the subject. If in doubt about whether a subject's care arrangements are suitable for inclusion, the investigator should discuss this with the medical monitor. At visits where the CDR or FAQ are conducted, caregivers or informants need to either attend the visit in person along with the subject or be able to be contacted by telephone at the time of the visit. The investigator will determine whether attendance in person is required or whether telephone contact will be suitable and will base this determination upon the functional ability of the subject among other factors.
 5. If receiving acetylcholinesterase inhibitor (AChEIs) or memantine, must have been on a stable dose for at least 12 weeks before the Baseline cognitive assessments at Visit 2, with no plans for dose adjustment in the foreseeable future. Treatment-naïve subjects can be entered into the study but there should be no plans to initiate treatment with AChEIs or memantine at the time of entry into the study.

6. Must have been on stable doses of all other permitted chronically used concomitant medications (ie, not related to their cognitive decline) for at least 4 weeks before randomization

9.3.2 Exclusion Criteria

Subjects who meet any of the following criteria will be excluded from this study:

1. Any neurological condition that may be contributing to cognitive impairment above and beyond that caused by the subject's AD pathology, including any co-morbidities detected by neurological examination or MRI
2. Modified Hachinski Ischemic Scale >4
3. History of transient ischemic attacks or stroke within 12 months of Screening
4. A history of epilepsy. Subjects with a history of seizures (not including a history of simple febrile seizures in childhood) within 10 years of Screening. Subjects with disturbance likely to be due to seizures within 5 years of Screening.
5. Significant pathological findings on the brain MRI at Screening, including but not limited to: more than 4 microhemorrhages (defined as 10 mm or less at the greatest diameter), any microhemorrhage which is symptomatic, a single macrohemorrhage greater than 10 mm at greatest diameter, an area of superficial siderosis, evidence of vasogenic edema, greater than 3 lacunar infarcts or a single infarct >2 cubic centimeters involving a major vascular territory, evidence of severe microangiopathy, evidence of cerebral contusion, encephalomalacia, aneurysms, vascular malformations, infective lesions or space-occupying lesions (eg, arachnoid cysts) or brain tumors (eg, meningioma).
6. Any psychiatric diagnosis or symptoms, (eg, hallucinations, major depression, or delusions) that could confound the MCI/Prodromal or mild AD diagnosis or could interfere with study assessments or procedures
7. A score of ≥ 8 on the 15-item Geriatric Depression Scale (GDS) at Screening
8. Abnormally low serum vitamin B12 (<LLN) levels for the testing laboratory (if subject is taking vitamin B12 injections, level should be at or above the LLN for the testing laboratory) at Screening
9. Thyroid stimulating hormone above the normal range. Other tests of thyroid function with results outside the normal range should only be exclusionary if they are considered clinically significant by the investigator. This applies to all subjects regardless of whether or not they are taking thyroid supplements.
10. Subjects with hepatic impairment, with total bilirubin greater than $1.5 \times$ upper limit of normal (ULN) or International Normalized Ratio (INR) greater than 1.7 at Screening or Baseline. Subjects with Gilbert's syndrome need not be excluded.
11. Any contraindications to MRI or PET scanning, including cardiac pacemaker/ defibrillator or ferromagnetic metal implants (eg, in skull; cardiac devices other than those approved as safe for use in MRI scanners). Subjects who require sedation for MRI or PET scanning as per local guidelines need not be excluded.

12. Any contraindications to lumbar puncture (LP) for CSF sampling (eg, lower spinal malformation on physical examination, local spinal infection or other abnormality, including but not limited to obesity)
13. Severe visual or hearing impairment that would prevent the subject from performing psychometric tests accurately
14. History of Ig deficiency or other immunodeficiency disorders (including subjects known to be human immunodeficiency virus positive)
15. Subjects with chronic viral hepatitis
16. A history of tuberculosis (TB). Subjects with no history of TB will be tested for previous TB exposure (eg, positive tuberculin skin test, interferon gamma release assay or other locally accepted tests) and a positive test will be exclusionary.
17. A history of ophthalmic shingles
18. A history of ocular herpes simplex virus (HSV) infection
19. Any live vaccine in the 3 months before randomization.
20. Any active infection within the last 4 weeks prior to randomization. For such cases, the timing of randomization can be extended (up to 4 weeks) to allow the infection to resolve; psychometric tests conducted at Visit 2 (eg, MMSE, CDR, etc) must be repeated.
21. Any chronic inflammatory disease that is not adequately controlled or that requires systemic or ocular immunosuppressive or immunomodulatory therapy. Subjects with:
 - a. Seasonal or perennial allergic rhinitis, asthma or chronic obstructive pulmonary disease where the condition is considered to be stable and adequately controlled by inhaled steroids need not be excluded.
 - b. Hashimoto's thyroiditis but who are stable on thyroid replacement therapy and not on systemic immunosuppressive therapy need not be excluded.
 - c. Cutaneous manifestations of immunological disease that do not require systemic immunosuppressive therapy or systemic immunomodulatory therapy need not be excluded (topical steroid treatment is permitted).
22. CD4 (T helper cells), CD8 (cytotoxic T cells), or CD19 (B cells) absolute counts below LLN and confirmed by a repeat test conducted 1 week after the initial test
23. Ig (IgG, IgA, or IgM) levels below the LLN
24. Clinically significant deviation from normal in physical examination, vital signs, or clinically laboratory tests at Screening or Baseline
25. A prolonged QT/ corrected QT interval (QTc) interval (QTc >450 msec) at Screening or Baseline as demonstrated by average QTc interval from triplicate ECGs. A history of risk factors for torsade de pointes (eg, heart failure, hypokalemia, family history of long QT Syndrome) or the use of concomitant medications that prolong the QT/QTc interval.
26. Any other abnormality of the ECG at Screening or Baseline (including QRS >110 msec, abnormal electrical axis, PR interval >220 msec and conduction abnormalities) considered clinically significant by the investigator
27. Left bundle branch block at Screening or Baseline
28. Persistent heart rate <50 or >100 beats per minute (bpm) at Screening or Baseline

29. Persistent systolic blood pressure (BP) >165 mmHg or <90 mmHg and diastolic BP >100 mmHg or <60 mmHg at Screening
30. History of cardiac arrhythmias. Subjects with other heart diseases (eg, ischemic heart disease, clinically significant valvular heart disease) that are not stably and adequately controlled, or uncompensated heart failure (New York Heart Association Class III and Class IV)
31. Type 1 or Type 2 diabetes mellitus that is not well controlled
32. Malignant neoplasms within 5 years before Screening (except for basal or squamous cell carcinoma in situ of the skin, or localized prostate cancer that did not require systemic therapy; these do not exclude the subject). Subjects who had malignant neoplasms but who have had at least 5 years of documented evidence of no active disease before Screening need not be excluded.
33. Medical conditions (eg, cardiac, respiratory, gastrointestinal, renal disease) that are not stably controlled, or which, in the opinion of the investigator(s), could affect the subject's safety or interfere with the study assessments
34. Hypopigmentation conditions (eg, albinism and vitiligo)
35. Known or suspected history of drug or alcohol dependency or abuse within 2 years before Screening, current use of recreational drugs or a positive urine drug test at Screening. Subjects who test positive in the urine drug screen need not be excluded if in the clinical opinion of the investigator, this is due to the subject taking prior/concomitant medications for a medical condition that is not exclusionary and not due to drug abuse.
36. Has a "yes" answer to the C-SSRS suicidal ideation questions 4 or 5, or any suicidal behavior assessment within 6 months before Screening, at Screening, or at the Baseline Visit; or has been hospitalized or treated for suicidal behavior in the past 5 years before Screening
37. Violations of the medical restrictions as specified in the Concomitant Medications section of the protocol
38. Planned surgery that requires general, spinal, or epidural anesthesia that would take place during the study. Planned surgery, which requires only local anesthesia and which can be undertaken as a day case without inpatient stay postoperatively, need not result in exclusion if in the opinion of the principal investigator this operation does not interfere with study procedures and subject safety.
39. Participation in any other interventional clinical study related to cognitive impairment within 6 months before Screening unless it can be documented that the subject was in a placebo treatment arm
40. Currently enrolled in another clinical study or used any investigational drug or device within 60 days or 5 half-lives of the investigational medication (whichever is longer) preceding informed consent
41. Hypersensitivity to the study drug or any of the excipients or to other BACE inhibitors, or to the PET tracer, or components of its formulation
42. Females who are lactating or pregnant (as documented by a positive beta-human chorionic gonadotropin [β -hCG] or human chorionic gonadotropin [hCG] test with a minimum sensitivity of 25 IU/L or equivalent units of β -hCG or hCG) at Screening or

Baseline. A separate baseline assessment is required if a negative screening pregnancy test was obtained more than 72 hours before the first dose of study drug.

43. Females of childbearing potential who:

- Had unprotected sexual intercourse within 30 days before study entry or who do not agree to use a highly effective method of contraception (eg, total abstinence, an intrauterine device, a double-barrier method [such as condom plus diaphragm with spermicide], a contraceptive implant, an oral contraceptive, or have a vasectomized partner with confirmed azoospermia) throughout the entire study treatment period or for 28 days after study drug discontinuation.
- Are currently abstinent, and do not agree to use a double-barrier method (as described above) or refrain from sexually active during the study treatment period or for 28 days after study drug discontinuation.
- Are using hormonal contraceptives but are not on a stable dose of the same hormonal contraceptive product for at least 4 weeks before dosing or who do not agree to use the same contraceptive during the study treatment period or for 28 days after study drug discontinuation.

(NOTE: All females will be considered to be of childbearing potential unless they are postmenopausal [amenorrheic for at least 12 consecutive months, in the appropriate age group, and without other known or suspected cause] or have been sterilized surgically [ie, bilateral tubal ligation, total hysterectomy, or bilateral oophorectomy, all with surgery at least 1 month before dosing]).

44. Males who have not had a successful vasectomy (confirmed azoospermia) or they and their female partners do not meet the criteria above (ie, not of childbearing potential or not practicing highly effective contraception throughout the study period or for 28 days after study drug discontinuation). No sperm donation is allowed during the study period and for 28 days after study drug discontinuation.

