9. Male subjects must have had a successful vasectomy (confirmed azoospermia) or they and their female partners must meet the criteria above (ie, not of childbearing potential or practicing highly effective contraception throughout the study period and for 30 days after study drug discontinuation). No sperm donation is allowed during the study period and for 30 days after study drug discontinuation.
10. Provide written informed consent
11. Willing and able to comply with all aspects of the protocol

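### Exclusion 44 negates both halves of the male contraception rule but keeps *or*, so as written it bars every man without a confirmed vasectomy

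*Protocol*

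**What the plan says.** The file holds two versions of the protocol. In the version whose Section 9.3.2 runs to 44 criteria, the list opens with "Subjects who meet any of the following criteria will be excluded from this study". Exclusion 44 then covers "Males who have not had a successful vasectomy (confirmed azoospermia) or they and their female partners do not meet the criteria above", and its parenthesis explains failing the criteria as "not of childbearing potential or not practicing highly effective contraception throughout the study period or for 28 days after study drug discontinuation". The inclusion list of that version (Section 9.3.1) has six items and no male contraception rule, so Exclusion 44 is the only statement of it there. Inclusion 3 reads "Male or female, age 50 to 85 years, inclusive at time of consent".

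The other version puts the rule in the inclusion list, as Inclusion 9 in the Synopsis and in Section 9.3.1: "Male subjects must have had a successful vasectomy (confirmed azoospermia) or they and their female partners must meet the criteria above". There, a partner not of childbearing potential is a way of meeting the criteria.

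Exclusion 29 of the 44-item list reads "Persistent systolic blood pressure (BP) >165 mmHg or <90 mmHg and diastolic BP >100 mmHg or <60 mmHg at Screening". The other version has the same wording as its Exclusion 28. Exclusion 24 separately covers "Clinically significant deviation from normal in physical examination, vital signs, or clinically laboratory tests at Screening or Baseline", with no numeric limit. Exclusion 33 covers medical conditions that are not stably controlled or that could affect safety.

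**The concern.** When a rule of the form *A or B* is moved from the inclusion list to the exclusion list, its negation is *not A and not B*. Exclusion 44 has *not A or not B*. Taken with the opening line of Section 9.3.2, it turns away a man whose couple fully meets the contraception criteria, simply because he has not had a vasectomy. The parenthesis adds to this, because it moves a partner not of childbearing potential from the qualifying side to the failing side.

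A site then has two courses. It can turn away men whom the inclusion form admits, or it can enrol men who on paper meet an exclusion criterion. Either way the rule that the text states is not the one the sponsor appears to have meant.

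Exclusion 29 raises a lesser question. Its systolic and diastolic limits each contain *or* and are joined by *and*, so two sites could classify the same reading differently.

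**Working it through.** No sample size, power or error rate is involved. The check is a truth table.

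**Exclusion 44, main clause.** Let V mean that a vasectomy is confirmed and C that the contraception criteria are met. Inclusion 9 admits a man if V or C. Exclusion 44 as written admits him only if neither *not V* nor *not C* holds, that is, if V and C.

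| V | C | Eligible under Inclusion 9 | Eligible under Exclusion 44 as written | Eligible with *and* |
|---|---|---|---|---|
| yes | yes | yes | yes | yes |
| yes | no | yes | **no** | yes |
| no | yes | yes | **no** | yes |
| no | no | no | no | no |

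The written rule disagrees with the inclusion form in 2 of 4 rows. With *and* it agrees in all 4. The third row matters most. The second may be rarely populated, because Exclusion 43 itself names a vasectomized partner with confirmed azoospermia among the highly effective methods.

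**Exclusion 44, parenthesis.** Let N mean that the partner is not of childbearing potential and P that highly effective contraception is practised. The inclusion form counts the criteria as met if N or P; its negation is *not N and not P*. The written parenthesis counts them as failed if N or *not P*.

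| N | P | Inclusion form | Parenthesis as written |
|---|---|---|---|
| yes | yes | met | **failed** |
| yes | no | met | **failed** |
| no | yes | met | met |
| no | no | failed | failed |

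Again 2 of 4 rows differ, both with a partner not of childbearing potential. Taken literally, the parenthesis would exclude a vasectomized man with such a partner as well.

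**Exclusion 29.** Three readings are possible:

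- Conjunctive: (systolic >165 or <90) and (diastolic >100 or <60).
- Strict and-before-or precedence: systolic >165, or (systolic <90 and diastolic >100), or diastolic <60.
- List of two separate limits: either value out of range.

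| BP (mmHg) | Conjunctive | Precedence | Either |
|---|---|---|---|
| 200/80 | not excluded | excluded | excluded |
| 85/70 | not excluded | not excluded | excluded |
| 130/110 | not excluded | not excluded | excluded |
| 130/55 | not excluded | excluded | excluded |
| 200/110 | excluded | excluded | excluded |
| 85/55 | excluded | excluded | excluded |
| 130/80 | not excluded | not excluded | not excluded |

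The readings agree when both values are out of range, as in the two such examples shown, and when neither is. They disagree on all four isolated abnormalities.

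**The case against.** The strongest reply is that this is a drafting slip whose intent is plain. The inclusion form elsewhere in the file shows what was meant, and sensible sites would apply that. Nothing in the primary analysis depends on it: Section 9.7.1.6.1 uses the Full Analysis Set, whose definition does not turn on eligibility. That reply stands as a limit on the consequences. It does not make the criterion right, since Exclusion 44 is the only male contraception rule in its version and any one exclusion is decisive.

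A reader might infer several stronger things that the documents do not support:

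- *That the trial would become nearly all female, or need a calculable number of extra screens.* The protocol gives neither the expected share of men nor a vasectomy rate. Its screening totals stand in the Synopsis of the version whose male criterion is correctly worded. Any such figure would also assume literal enforcement.
- *That Exclusion 44 contradicts Inclusion 3.* An exclusion that narrows which men are eligible, while leaving some eligible, does not contradict a statement that both sexes may enter.
- *That the Per Protocol set is compromised.* Section 9.7.1.2 leaves its evaluability criteria to the statistical analysis plan, which is not shown, and uses the set for a sensitivity analysis. This is only a risk.
- *That Exclusion 29 plainly requires both abnormalities and so defeats its own limits.* That is one reading of three. Exclusions 24 and 33 can still remove an isolated abnormality by the investigator's judgement, so what is unclear is the objective cut-off.

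**Conclusion.** Exclusion 44 is wrong as written. Read with the opening line of Section 9.3.2, it bars every man without a confirmed vasectomy, including those whose couple meets the contraception criteria, and its parenthesis treats a partner not of childbearing potential as a failure. The main clause misclassifies 2 of 4 combinations against the sponsor's own inclusion form, and the parenthesis another 2 of 4. The conclusion assumes only that the inclusion form states the intended rule; no prevalence figure is needed.

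Exclusion 29 is ambiguous rather than wrong, and is a secondary point. Neither defect is shown to affect sample size, power, error rates or the primary analysis. The case for correcting them is that eligibility rules should state what sites are meant to apply, and that avoidable eligibility deviations should not arise.

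**What to change.** Reconcile Exclusion 44 with Inclusion 9 of the other version (Synopsis and Section 9.3.1). Join the two negated conditions with *and* in place of *or*. Correct the parenthesis so that a partner not of childbearing potential is no longer listed as a failure; the logical complement of the inclusion form is a partner who is of childbearing potential *and* is not covered by highly effective contraception. Keep the sperm-donation sentence, the 28-day period and all other terms. This restores the sponsor's own rule and drafts no new contraception requirement.

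For Exclusion 29, the sponsor should state which of the readings applies and reconcile the wording with Exclusions 24 and 33. No limit is questioned or proposed here.

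The cost is a wording change in an amendment and a note to sites. Study procedures, numbers and analyses stay as they are.
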